### Duration of anesthetic effects

The secondary endpoint of the duration of anesthetic effect in minutes from the onset of anesthetic effect to the time point when pinch pain resumes is defined in Section 2.6.2. This endpoint will be compared for between-group differences, using a 2-way ANOVA model with treatment (the effect of interest) and study eye side as the effects. The study-eye-side effect is used as a blocking factor in the model to control the potential treatment differences among the sites.

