9.4.6 Analysis of Efficacy

Analyses will be performed primarily on the ITT population and will be repeated on the PP population to determine robustness of results. For the primary efficacy endpoint of the proportion of subjects with no pain at 5 minutes, a Pearson chi-square test will be used for the comparison of the two proportions from the two treatment groups. In addition, a two-sided 95% confidence interval for the difference in response rates between the two treatment groups will be calculated. If the lower limit of the 95% confidence interval is greater than 0 and the P value is statistically significant ($P < 0.05$), then superiority of AG-920 over the placebo will be claimed.

Sub-group analyses based upon pre-study characteristics such as sex, iris color, age, and race may be completed to further investigate the efficacy and safety measures.

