### 2.9.1 Primary efficacy analysis

The primary efficacy endpoint for this study is the proportion of subjects with anesthetic response defined as no pain at 5 minutes post application of the dose. The definition of the primary efficacy endpoint is given in Section 2.6.1. The non-parametric Cochran-Mantel-Haenszel (CMH) test with adjustment for study eye side will be used to examine the difference in proportion of subjects with anesthetic response at 5 minutes post dose between the active treatment group and placebo group. If the proportion of subjects (expressed as a percentage) is higher in the AG-920 group and the  $P$  value is statistically significant ( $P \leq 0.05$ ), then superiority of AG-920 over placebo will be claimed.

Between-group difference and its 95% confidence interval (CI) in the proportion of subjects with anesthetic response (yes=1) vs. non-response (no=0) will be calculated using a two-way analysis of variance (ANOVA) model with treatment (the effect of interest) and study eye side as the effects. The study-eye-side effect is used as a blocking factor in the model to control the potential treatment differences among the study eye sides.

The primary efficacy analysis will be performed for the ITT population, which will include all of the randomized subjects who received the complete application of one study dose (i.e., two drops). The analysis model adjusts for the effect of the study eye side. The study-eye-side by treatment interaction will be examined through the summary descriptive statistics of subjects with anesthetic response for each study eye side.

Prior to the determination of the primary efficacy variable, handling of missing values that occur prior to or at 5 minutes post dose is described in Section 2.8.

The primary efficacy endpoint will also be analyzed for the PP population as well as for subgroups of the ITT population, such as male vs. female, Caucasian vs. Non-Caucasian, age groups, and iris color dark brown vs. other colors.

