#### Onset of anesthetic effects

The secondary endpoint of the onset of anesthetic effect in minutes from time of dose application completion to no pain within 5 minutes post dose is defined in Section 2.6.2. This endpoint will be compared for between-group differences, using a 2-way ANOVA model with treatment (the effect of interest) and study eye side as the effects. The study-eye-side effect is used as a blocking factor in the model to control the potential treatment differences among the study eye sides. For the accuracy and appropriateness of the analysis, those subjects who are censored on (or not achieving) the onset of anesthetic effect will be excluded from statistical analysis.

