#### **4.5 Efficacy Results and Tabulations**

##### **4.5.1 Results of primary efficacy analysis**

Descriptive and inferential statistics on the ITT population of the proportion of subjects with anesthetic response at 5 minutes post dose will be presented in Table 2.1.1.

For the PP population, the results of the same proportion analysis on the number of subjects with anesthetic response at 5 minutes post dose will be presented in Table 2.1.2.

The by-site summary of descriptive statistics of the number of subjects with anesthetic response at 5 minutes post dose will be presented in Table 2.1.3.

The results of the proportion analysis on the number of subjects with anesthetic response at 5 minutes post dose will be presented for the sub-populations of men vs. women in Tables 2.2.1 and 2.2.2; for 34 years or younger vs. 35 years or older in Tables 2.2.3 and 2.2.4; for Caucasian vs. Non-Caucasian in Tables 2.2.5 and 2.2.6; and, for iris color dark brown vs. other colors in Tables 2.2.7 and 2.2.8.

Individual subjects' primary efficacy data (i.e., pinch pain response) assessed post dose on Day 1 by Investigator, with and without imputation, will be listed by treatment for the ITT population (Listing 6).

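### SAP 2.9.2 says the study-eye-side factor controls differences among sites, which it cannot do; no efficacy model contains site, and adding it is a cheap improvement if two sites enrol

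*SAP*

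**What the plan says.** **Duration (SAP 2.9.2).** The groups are compared "using a 2-way ANOVA model with treatment (the effect of interest) and study eye side as the effects". The next sentence reads: "The study-eye-side effect is used as a blocking factor in the model to control the potential treatment differences among the sites".

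**Onset (SAP 2.9.2).** The model is the same, but there the eye-side effect is "used as a blocking factor in the model to control the potential treatment differences among the study eye sides". SAP 2.9.1 uses that ending for the primary endpoint as well.

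**Primary endpoint.** SAP 2.9.1: "The non-parametric Cochran-Mantel-Haenszel (CMH) test with adjustment for study eye side will be used". The difference and its confidence interval come from a "two-way analysis of variance (ANOVA) model with treatment (the effect of interest) and study eye side as the effects". Protocol 9.4.6 has no adjustment at all: "a Pearson chi-square test will be used for the comparison of the two proportions from the two treatment groups".

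**Site.** The only efficacy output by site in the readable text is in SAP 4.5.1: "The by-site summary of descriptive statistics of the number of subjects with anesthetic response at 5 minutes post dose" (Table 2.1.3). SAP 4.5.2 names none for onset or duration; the table list in SAP 7 is redacted, so it cannot settle the matter. The Protocol Summary allows one or two US sites. Protocol 3.1 has study staff perform the pinch. Protocol 5 randomizes the study eye. Neither Protocol 3.5 nor SAP 2.4 describes stratification or blocking by site.

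**The concern.** A reader of the duration paragraph would conclude that site has been dealt with. It has not: the model has no site term, and a factor randomized within each site cannot stand in for one.

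The wider question is whether site belongs in the models. The endpoint is a yes/no answer to a forceps pinch given by hand, so pinch technique is a plausible source of variation between sites. The documents give no reason why right versus left eye should predict pain, yet eye side is the only adjustment factor. If two sites enrol and differ, the between-site variation stays in the comparison and precision that was available is given up.

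**Working it through.** **1. Wording.** Three sentences describe the same blocking factor. Two end with eye sides (primary, onset) and one with sites (duration). All three models contain treatment and eye side only. Eye side is randomized per subject, so it is independent of site in expectation and absorbs none of the between-site variance.

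**2. The plan's own power (SAP 2.5).** Inputs: 60 per arm, 15% versus 40%, two-sided 0.05, chi-square without continuity correction.
- Pooled proportion: (0.15 + 0.40)/2 = 0.275
- SE under the null: √(2 × 0.275 × 0.725/60) = 0.0815
- SE under the alternative: √((0.15 × 0.85 + 0.40 × 0.60)/60) = 0.0783
- z = (0.25 − 1.96 × 0.0815)/0.0783 = 1.15, so power is 87.6%. The stated 88% reproduces.

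**3. Primary test with and without site.** The documents give no site effect, so the site rates below are assumptions. Setup: two sites of 60, eye side random 1:1. The CMH statistic is [Σ(a − n₁m₁/n)]² / Σ[n₁n₀m₁m₀/(n²(n − 1))], summed over strata without continuity correction and compared with 3.84. In each stratum n is the number of subjects, n₁ and n₀ the numbers on active and placebo, m₁ and m₀ the responders and non-responders, and a the active responders. There were 20,000 trials per row, except 8,000 in the rows marked *. *Free* means arms are balanced overall but not within site; *balanced* means 30 per arm at each site.

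| Placebo, active rates (site A/site B) | Arms | Eye side only | Site only | Eye side × site |
|---|---|---|---|---|
| 15/15, 40/40 | free | 87.7% | 87.7% | 87.3% |
| 15/15, 40/40 | balanced | 88.1% | 88.3% | 87.7% |
| 5/25, 30/50 | free | 88.1% | 89.9% | 89.5% |
| 5/25, 30/50 | balanced | 88.6% | 90.2% | 89.4% |
| 2/28, 27/53 | free | 87.8% | 91.0% | 90.4% |
| 2/28, 27/53 | balanced | 89.2% | 91.4% | 90.9% |
| 2/28, 20/60 * | free | 87.6% | – | 91.7% |
| 2/28, 20/60 * | balanced | 89.3% | – | 91.9% |

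A separate 40,000-trial check of the 2/28, 20/60 case with free allocation gave 87.7% for eye side only, 92.4% for site only and 91.9% for eye side × site.

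Gains from the four eye-by-site strata run from 0.8 points (5/25, 30/50, balanced) to 4.1 points (2/28, 20/60, free). With site as the only stratum and free allocation they run from 1.8 to 4.7 points. With no site difference the four strata cost about 0.4 points here, and no more than about 0.7 in repeated runs.

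**4. Type I error, same setup, no drug effect.**

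| Site rates | Arms | Eye side only | Eye side × site |
|---|---|---|---|
| 5/25 | free | 5.0% | 5.0% |
| 0/30 | free | 4.9% | 5.3% |
| 5/25 | balanced | 4.1% | 5.1% |
| 0/30 | balanced | 3.1% | 4.9% |
| 5/60 * | balanced | 1.5% | 4.7% |

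The eye-only test is nominal under free allocation and conservative under within-site balance. The last row averages 32.5% response, well above the planned 15% on placebo.

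**5. Duration ANOVA.** Expected responders are 0.15 × 60 = 9 and 0.40 × 60 = 24. In units of the within-site SD, the SE of the treatment difference is √(1/9 + 1/24) = 0.39. If site is left out and responders split evenly between sites, a site gap of g SD raises the residual SD to √(1 + g²/4). The SE becomes 0.44 at g = 1 and 0.55 at g = 2. Simulation (4,000 trials, assumed treatment effect 1 SD, site independent of arm among responders):

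| Site gap | Power with eye side | Power with site |
|---|---|---|
| 0 SD | 68% | 67% |
| 0.5 SD | 64% | 67% |
| 1 SD | 58% | 68% |
| 2 SD | 40% | 68% |

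**The case against.** The strongest reply is that this is one wrong word. The duration model itself is unambiguous and would be run as intended. That stands: nothing in the documents shows that a site term was planned and then lost, and the duration sentence should not be read as evidence that the sponsor meant to adjust for site.

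It is also fair that leaving site out is a choice on precision rather than an error. A reader might infer that the trial is underpowered, that the primary result could be biased, or that false positives become more likely. None of these follows. Eye-only power stays near 88% in every scenario; what is lost is a possible gain. Treatment is randomized, and type I error does not rise.

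A reader might also infer that the eye-only test is conservative. That requires arms balanced within site. SAP 2.4 says packs are drawn from those available at a site, which does not establish balance.

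Nor do the documents show that technique differs by site. Protocol 6.4.3 fixes the question, tells subjects that pressure is not pain, and says the pinching method is detailed separately. Table 2.1.3 would reveal a large divergence in the primary response. What survives is that this table adjusts nothing, and that the claim of control in the duration paragraph is untrue as written.

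**Conclusion.** The duration sentence is wrong and should be corrected; it is most likely a carry-over slip. The absence of site from every efficacy model is a modest weakness, and it matters only if two sites enrol.

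For the primary endpoint the benefit of adding site is about 1 to 4 points of power with eye-by-site strata, or about 2 to 5 with site as the only stratum and arms not balanced within site. Both ranges assume response rates 20 to 40 points apart between sites. If arms happen to be balanced within site, adding it also restores nominal type I error.

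For duration the benefit could be larger, about 10 points at an assumed 1 SD gap, but both the gap and the treatment effect are assumptions. Duration uses responders only, so the protection of randomization is weaker there; the simulation assumes that responders' site is unrelated to arm.

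This is a cheap improvement, not a threat to the primary conclusion.

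**What to change.** Before unmasking:

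1. In SAP 2.9.2, Duration, change the end of the blocking-factor sentence so that it refers to study eye sides, as in 2.9.1 and the onset paragraph.
2. State that, if two sites enrol, the primary CMH test is stratified by site as well as study eye (four strata, about 30 subjects each if the sites are equal), and that site is added as a factor in the ANOVAs for the primary difference, onset and duration.
3. Reconcile this with Protocol 9.4.6. The SAP's CMH test already departs from the protocol's unadjusted chi-square, and adding site moves it further. Name one test as primary and record the reason for the change.

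The cost is SAP wording and one more variable, which is already held because SAP 2.9 builds the site number into the subject ID. The statistical downside is at most about 0.7 points of primary power if the sites do not differ. If only one site enrols, item 2 has no effect. Deciding on site adjustment after results are seen would be post hoc, so the rule has to be written in advance.

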### **2.9.3 Safety analysis**

#### Treatment Exposure

Frequencies of exposure to the study medication will be calculated based on the number of drops the subject has received over the course of the study. Frequencies of exposure will be categorized as the following: 1 drop and 2 drops. Frequencies of exposure will be summarized by treatment for the safety population defined in Section 3.1, as well as for each gender group.

Compliance rates will be calculated by dividing the number of drops received by the number of drops that should have been given during the application of dose. Compliance rates will be summarized.

#### Early Termination

Subject disposition will be summarized by treatment and will be listed for those subjects who are terminated early. This listing will include demographic variables, treatment assigned, number of drops received, termination time, and the primary reason for early termination.

#### Adverse Events

Adverse events will be coded for preferred terminologies using Medical Dictionary for Regulatory Activities (MedDRA). AE will be grouped into pre-treatment AE and treatment-emergent AE and post-treatment AE and will be reported separately, based upon the start date and time of the events, the start date and time of the treatment.

Adverse events will be defined as the pre-treatment AEs if they occur prior to the treatment start date and time; as the treatment-emergent AEs if they occur on or after the treatment start date and time and before the next day; and as the post-treatment AEs if they occur after the treatment date.

Frequency of the treatment-emergent AEs will be calculated for each body system, by preferred terminology, by treatment group, for number of subjects and percentage reporting the event. The severity of the adverse events and the relationship to the investigational product will be summarized for each body system and preferred terminology by treatment group. Withdrawals due to adverse events will be summarized for each body system and preferred terminology by treatment group and will be listed with demographic variables for individual subjects.

Serious adverse events (SAE) (including deaths) will be listed for individual events.

Narratives will be provided for all deaths, non-fatal serious adverse events, and subjects withdrawn due to adverse events.

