8 ASSESSMENT OF SAFETY

8.1 *Specification of safety parameters*

The assessment of safety and tolerability will be evaluated by:

- BCVA (ETDRS)
- Biomicroscopy and external eye exam of anterior segment including evaluation of cornea, conjunctiva and anterior chamber.
- AEs (post treatment)
- AEs will be collected at every visit. See Section 8.3 for details on collection and reporting of AEs.

Screening only:

- Intraocular pressure
- Urine pregnancy test for females of childbearing potential

8.2 *The methods and timing for assessing, recording, and analyzing safety parameters*

Methods may be found in Table 1 and Appendix 1.

8.3 *Adverse events²*

All AEs occurring after the first dose of IMP and throughout the remainder of the study period (Follow-up Phone Call) will be considered TEAEs and must be documented on the relevant Electronic Data Capture (EDC) pages and in the source documents. Whenever possible, the diagnosis, if available, and not the symptoms should be reported as the AE. AEs and Serious Adverse Events (SAEs) will be coded according to the Medical Dictionary for Regulatory Activities (MedDRA).

Documentation of adverse events/adverse reactions includes start date and stop date, severity, action(s) taken, seriousness and outcome.

² Note: This section is referenced to 21 CFR 312.32 (IND safety reports), updated as per “Investigational New Drug Safety Reporting Requirements for Human Drug and Biological Products and Safety Reporting Requirements for Bioavailability and Bioequivalence Studies in Humans (Fed Reg 2010: 75 (188): 59935-59963).

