9.4.8 Adverse Events

Verbatim descriptions of AEs will be mapped to MedDRA thesaurus terms and be presented in a data listing. Treatment emergent AEs, those that occur after the first dose of study medication, will be summarized by treatment group using frequency counts and percentages for each system organ class (SOC) and preferred term (PT) within each SOC. Summaries will be presented separately for ocular and non-ocular AEs. These summaries will also be presented by the relationship to the Investigational Medical Product (related, unrelated) and by severity of the AE (mild, moderate, severe). Fisher's exact test will be used to test the difference in proportions of subjects with each AE between treatment groups (SOC and PT).

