### **2.2 Description of Trial Design**

This is a Phase 3, randomized, placebo-controlled, double-masked, parallel-group design study of safety and anesthetic efficacy of AG-920 topical drop versus placebo in healthy subjects. The study will evaluate the safety and anesthetic efficacy following one dose of Articaine Sterile Topical Ophthalmic Solution (AG-920), in comparison with placebo. Eligible subjects will be randomized in a 1:1 ratio to receive a single dose of AG-920 or matching placebo into one eye, designated as subject's study eye. The application of one single dose of AG-920 involves two drops 30 seconds apart into the subject's study eye.

The study consists of two visits and a follow-up phone call: one screening visit on Day -2 (Visit 1), one baseline/assessment visit on Day 1 (Visit 2), and one follow-up phone assessment on Day 2-5 (Phone Follow-Up).

Following the screening visit, eligible subjects will return to the clinic on Day 1 to have their study eye randomly assigned (right eye=OD or left eye=OS) and to be randomized to receive the study medication into the study eye. Subjects will undergo a conjunctival pinch procedure, and the pain associated with the pinch will be rated. Dosing of the study medication and conjunctival pinch procedure will be performed by the study staff.

To assess the anesthetic effect of the study medication, all subjects will be pinched at 20, 40, 60 seconds and 5 minutes post dose, defined as after the second drop of the dose application. If the subject feels no pain at 5 minutes, the subject will be considered "anesthetized." Pinching of anesthetized subjects will resume at 10 minutes and pinching will continue every five minutes for up to 30 minutes or until pain resumes. If the subject experiences pain 5 minutes post dose, pinching will be concluded and this subject will be considered to NOT have reached anesthesia.

All subjects who are randomized and who receive the study medication on Day 1 will be followed up with a phone call to on Day 2-5 for safety assessment.

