### **2.6.3 Safety measures**

Adverse events (AEs) are recorded at each visit and at follow-up phone call. When applicable, adverse events will be noted specifically in association with the study and non-study eyes.

Best corrected visual acuity (BCVA) and biomicroscopy (Slit-Lamp) and external eye exam are performed at each visit.

A urine pregnancy test will be performed at screening for all female subjects of child-bearing potential.

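### SAP 2.9.3 ends the TEAE window on the dosing day, against protocol 8.3 and against the SAP's own Tables 4.3.1 to 4.3.3

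*SAP*

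**What the plan says.** SAP 2.9.3 (Adverse Events) sorts events into three classes by onset. Events before treatment are pre-treatment. The second class is defined by the words "as the treatment-emergent AEs if they occur on or after the treatment start date and time and before the next day". Every later onset goes to a third class, which the SAP describes in these terms: "as the post-treatment AEs if they occur after the treatment date". The three classes are to be reported apart from each other.

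Protocol 8.3 sets a longer window: "All AEs occurring after the first dose of IMP and throughout the remainder of the study period (Follow-up Phone Call) will be considered TEAEs". Protocol 9.4.8, in the statistics section, says "Treatment emergent AEs, those that occur after the first dose of study medication, will be summarized by treatment group"; it names no end point and has no end-of-day limit. Protocol 6.5 places the call on Days 2 to 5, 24 to 96 hours after dosing.

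Elsewhere the SAP treats the call as part of the safety follow-up. Section 2.2 says that treated subjects "will be followed up with a phone call to on Day 2-5 for safety assessment", and section 2.6.3 says "Adverse events (AEs) are recorded at each visit and at follow-up phone call". SAP 5.3 then tabulates TEAEs by whether onset was on or off the dosing day: Table 4.3.1 for all TEAEs, 4.3.2 for the study eye and 4.3.3 for the non-study eye.

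**The concern.** TEAEs, and withdrawals due to them, are among the named secondary endpoints (protocol section 2). The SAP shortens the window that defines them and does not say that it departs from the protocol. A programmer cannot follow both 2.9.3 and the on/off-day split in 5.3.

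If 2.9.3 governs, events starting on Days 2 to 5 drop out of the TEAE incidence tables (4.2.2, 4.2.3, 4.2.5, 4.2.6). As SAP 5.3 words them, they also drop out of the severity and relationship table (4.4.1) and the SAE summaries (4.4.3, 4.4.5, 4.4.7). The early-termination tables are hardly affected, since only the call remains after Visit 2. Taken alone, the earlier end point can only lower a TEAE rate or leave it unchanged. If the conflict is left until after unmasking, someone must choose between two definitions with the results in view.

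A smaller point goes with it. SAP 2.9.3 says "The severity of the adverse events and the relationship to the investigational product will be summarized for each body system" and "Withdrawals due to adverse events will be summarized for each body system and preferred terminology by treatment group", which reads as all adverse events, while SAP 5.3 confines the matching tables to TEAEs.

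**Working it through.** The plan states no figure to reproduce here, so the check is on the definitions, followed by the size of their effect.

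**1. The two rules side by side**

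| Onset | SAP 2.9.3 | Protocol 8.3 |
|---|---|---|
| Day 1, after dosing starts | TEAE | TEAE |
| Day 2 up to the call | post-treatment | TEAE |

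**2. The off-dosing-day category.** There is one dosing day (protocol 1.3: a single treatment). An off-day onset is therefore either before Day 1, which is pre-treatment, or after Day 1, which SAP 2.9.3 calls post-treatment. Neither is a TEAE, so the category is empty whatever the hour of dosing. As an example, take a 10:00 dose (assumed) and onsets at half-hour steps from 0 to 96 h, which gives 193 points:

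- 28 points fall on the dosing day and are TEAEs under both rules.
- 193 − 28 = 165 points fall later. They are TEAEs under the protocol and post-treatment under the SAP.
- SAP TEAEs off the dosing day: 0.

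Reading the SAP limit as 24 hours does not help, because its post-treatment class is set by the treatment date.

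**3. Window length.** The documents give no clock times; dosing between 08:00 and 17:00 is assumed. The SAP window is 24 minus the hour of dosing:

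- 08:00: 16 h; 12:00: 12 h; 17:00: 7 h.
- Protocol window: 24 to 96 h.
- Share kept: at most 16/24 = 67%, at least 7/96 = 7%. These pair opposite extremes, and they are shares of hours, not of events.

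The SAP rule also depends on the clock. An event 10 h after an 08:00 dose (18:00, same day) is a TEAE. One 10 h after a 17:00 dose (03:00, next day) is not.

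**4. Effect on rates.** With 60 per arm in the safety population (the planned size), k subjects whose only qualifying event starts on Days 2 to 5 change the arm's TEAE rate by k/60:

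- k = 0: 0; k = 1: 1.67; k = 2: 3.33; k = 3: 5.00 percentage points.

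**5. The 5% cut-off in Table 4.2.3.** A preferred term is shown if it exceeds 5% in either arm. At n = 60, 4/60 = 6.67% is shown and 3/60 = 5.00% is not. At n = 59, 3/59 = 5.08% is shown and 2/59 = 3.39% is not. One reclassified subject can therefore remove a term, provided the other arm is also at or below 5%. The counts are illustrative, because the documents give no expected adverse event rates.

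**The case against.** The strongest reply is that no event is lost. SAP 2.9.3 commits to reporting post-treatment events as their own class. The overall summaries (Tables 4.1.1 and 4.1.2), Listings 7 to 9 and the narratives are not limited to TEAEs. The text of SAP 5.3 passes over Table 4.2.4 and the table list is redacted, so a post-treatment table may well exist. This stands: events are relabelled, not dropped from the report. It does not explain the on/off-day split in 5.3, which presupposes TEAEs after Day 1.

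A programmer would probably query an empty column rather than deliver it. That is likely, but the SAP gives no precedence between 2.9.3 and 5.3, so the answer would be settled outside the plan.

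The impact may also be small. The expected reactions in protocol 1.2 are transient stinging, burning or redness around instillation, so most events should start on Day 1. This stands too, and it is why shares of window hours must not be read as shares of events.

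The wording on severity and withdrawals in 2.9.3 can be read as continuing the preceding sentence on TEAEs. That reading is open, so this part is a request for consistent wording and carries little weight.

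**Conclusion.** The concern holds. SAP 2.9.3 conflicts with protocol 8.3, adds a limit that protocol 9.4.8 does not have, and makes the off-dosing-day category of Tables 4.3.1 to 4.3.3 empty by definition. That conclusion rests on the text alone and needs no assumption.

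The practical size is uncertain: 1.67 percentage points of an arm's TEAE rate per affected subject at 60 per arm, with the number of such subjects unknown and possibly zero. The window lengths of 7 to 16 h rest on assumed dosing times. Only safety reporting is affected. It should be fixed, because by-arm TEAE tables built on 2.9.3 would not match the protocol's definition.

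**What to change.** Before database lock, redefine TEAEs in SAP 2.9.3 as events with onset from the start of treatment through the follow-up call, as in protocol 8.3. Keep the on/off-day split in Tables 4.3.1 to 4.3.3, which then works as written. Keep the SAP's existing rule of classifying by onset, not by date of report, so that only onsets after the call fall outside the TEAE class.

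The same edit should state where the window ends for a subject who is never reached by phone. It should also say how an SAE with onset after the call is shown, since protocol 8.3.3 extends SAE reporting to four weeks after dosing. Use one scope, TEAEs or all adverse events, for severity, relationship and withdrawals in both 2.9.3 and 5.3.

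The cost is a few sentences and one derivation flag, with no new data. The only downside is that TEAE rates may look slightly less favourable.
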